5.2 EXCLUSION CRITERIA

An individual who meets any of the following criteria will be excluded from participation in this study:

Exclusion Criteria:

- (1) Greater than moderate disorganization on the PANSS (P2-Disorganization item >5)²⁶ because disorganized patients have had poorer outcomes in prior blended interventions in our lab due to difficulty learning to use mobile devices;
- (2) DSM-5 alcohol or substance dependence in past 3 months based on the SCID;
- (3) Level of care required interferes with outpatient therapy (e.g., hospitalized; severe medical illness); and
- (4) Unable to adequately see or manually manipulate a smartphone.

This study will include individuals between the ages of 18 and 65. Children under the age of 18 are excluded for several reasons. Since the key outcome of the iTEST intervention is independent functioning, the research topic is not relevant to many children who reside with family members and who are not expected to achieve milestones of independence as are adults. Moreover, the mechanisms underlying introspective accuracy have not been fully evaluated in children with psychotic disorders, and so children with psychotic disorders represent a unique treatment population that is different from the adult patient population that attends outpatient community mental health clinics. At this point it is unclear if the treatment needs of children mirror those of adults. The upper end of the included age range is 65 years. This is due to a number of reasons including the upper limit on the available normative data for certain assessment measures and the need to avoid a confound with age-related physical declines in functioning. It would also be necessary to tailor the mobile application and adapt the in-person intervention to the unique needs of older adults (e.g., visual and hearing impairments, ageist beliefs/self-stigma, age-related role changes, loss and isolation, greater severity of cognitive impairments).

We considered a broader transdiagnostic focus but our preliminary data on direct comparisons strongly suggest people with psychotic disorders have significantly more profound deficits in IA²⁷, notably in responsiveness to feedback²⁸, than do people with bipolar disorder

5.3 LIFESTYLE CONSIDERATIONS

Not Applicable

5.4 SCREEN FAILURES

Screen failures are defined as participants who consent to participate in the clinical trial but are not subsequently assigned to the study intervention or entered in the study. A minimal set of screen failure information is required to ensure transparent reporting of screen failure participants, to meet the Consolidated Standards of Reporting Trials (CONSORT) publishing requirements and to respond to queries from regulatory authorities. Minimal information includes demography, screen failure details, eligibility criteria, and any serious adverse event (SAE).

Individuals who do not meet the criteria for participation in this trial (screen failure) because of a substance use disorder or disorganization on the PANSS may be rescreened after a minimum of one

month which is the duration follow back on these instruments. Rescreened participants should be assigned the same participant number as for the initial screening.

Screen failures will be provided with referrals to mental health services in the community by way of a resource list that contains information about walk-in, free and low cost services through the San Diego County Mental Health department.

6 STUDY INTERVENTION

Leave blank. Text should be included under the relevant subheadings below.

6.1 STUDY INTERVENTION(S) ADMINISTRATION

Leave Blank. Text should be included under the relevant subheadings below.

6.1.1 STUDY INTERVENTION DESCRIPTION

iTEST consists of several integrated components – coaching and mobile web-based software

Coaching: iTEST begins with a 60-minute Introductory Coaching session and then weekly for 5 weeks thereafter. These sessions can be delivered remotely or in-person, per preference of the participant. Sessions are scripted and manualized (see *Fidelity* below) as our prior blended health interventions^{21-23,29}. The introduction session provides the basis of iTEST (60 minutes) through psychoeducation on IA in functional recovery, application to compensatory strategies and goal setting, with a personalized goal identification activity derived from prior work^{23,30}. Thereafter, coaching in iTEST involves the following structure: 1) review and feedback on mobile training adherence and IA scores (15 minutes), 2) training in application of improved IA to everyday activities (30 minutes), and 3) training, selection, and application of compensatory strategies to weekly goals (15 minutes). Each 60 min session begins with reviewing the week's IA scores and problem solving about any barriers to engagement. For the remainder of the session, Coaches develop action plans that incorporate IA concepts. Materials are derived and adapted from Action-Based Cognitive Remediation³⁰. In each meeting, the Coach collaborates to identify and plan two functionally relevant activities that involve at least some cognitive challenge (*“one thing you want to do and one thing you have to do in the next 2 weeks”*). The pair collaborates to generate a list of action steps via a cognitive “walkthrough” simulating the initiation, engagement, and completion of the goal-linked social or non-social activities. Challenges due to memory, social reasoning, or attention failures are thus minimized, and the Coach demonstrates and trains in use of compensatory strategies, including setting reminders, scheduling via calendars, and asking (rather than inferring) others' emotions and/or intentions. These are personalized (e.g., use of electronic or paper-based techniques). During the walkthrough of action steps, queries include identification of cues or other evidence that signifies progress or setbacks, which align with IA training in increasing attention to external cues (vs. self-generated impressions). The tasks of generating action steps and selecting compensatory strategies gradually shifts toward becoming fully participant driven. Coaching intensity is consistent with our past studies²¹⁻²³.

Fidelity and quality assurance for coaching: Participants are asked to provide consent for audio recordings for fidelity monitoring of coaching sessions. Audio files are then reviewed by [name] and other individuals who are part of the coach supervision team (who are included as personnel on the IRB). Audio files are kept on a secure server and rated according the process below. Once rated, audio

files are destroyed.

We will conduct a two-day training workshop for coaches and provide weekly supervision to the coaches. All treatment sessions, messaging, telephone contacts (iTEST and CC) are rated according to fidelity to the iTEST treatment model. Sessions will be rated using an adapted version of the *Cognitive Therapy Rating Scale for Psychosis (CTS-Psy³¹)*. Sessions have been alerted to capture the core elements of iTEST. We will evaluate these fidelity scores based on a threshold of 80% adherence to the iTEST model, and scores below 80% adherent would lead to discussions with the coaches to correct/modify their approach so as to improve fidelity. Coaches will be bachelor's or master's level with comparable experience to a community clinician and will receive weekly 1-hour supervision from [name].

Automated Drill-and-Practice Training with Mobile Web-based Platform: For onboarding, device training is provided on how to operate and charge the smartphone, the meaning of questions and response choices, personalizing training alerts, and how to access crisis lines. The participant completes three practice rounds of iTEST in which the focus on IA and scoring is explained. If participants do not evidence understanding of the basis of scoring (e.g., mistake performance vs. IA accuracy as the basis of scoring), additional rounds of practice will be completed. Next, the coach collaborates on a training schedule (time of day, preferred day off) and identifies potential barriers (e.g., interruptions, fatigue) and accompanying solutions, along with facilitators to practice (e.g., small self-selected available non-monetary rewards for completion). Finally, a schedule is developed for follow-up contacts and review of progress. Daily training will begin the day after this initial session.

Training involves prompts 6x per week to engage in the Task-Based training, which lasts 10-15 minutes per session and consists of three blocks each of IA on verbal memory and emotion recognition. The reason to deliver task-based training 6x per week was to provide one day off (which can be selected by the participant). Alarms can be silenced for 30-minute intervals (e.g., driving, appointments). If a participant misses a session, they will receive 2 reminders that day to complete it. If they miss two consecutive days (or one day during the first week), participants will be contacted by their Coach to engage in problem solving and motivational support. Our previous data on remote adherence suggested that early adherence was highly predictive of total adherence ($r=.80$)³², so daily first week outreach will occur in case of non-adherence.

Our web-based smartphone compatible software is built around our previously validated VLMT and METER tasks. This flows from a) introductory/instruction screens, b) presentation of stimuli, c) performance assessment (initially with feedback on correctness), and d) IA queries (how many words/faces correct, confidence) e) feedback about IA. Items b-e are then repeated for the second and third trials of the tasks. Stimuli include variable numbers of words or faces with the number of stimuli randomly ordered per session and derive from a large normed corpus so that stimuli are not repeated. Training is graduated in four steps: (1) The first skill is correctly identifying the number of stimuli presented (task awareness); (2) After 3 consecutive sessions in which the number of stimuli is correctly identified, participants are provided *trial-by-trial* feedback on correctness of response and scoring is based on correct assimilation of trial-by-trial feedback to global estimation of performance (e.g., “you indicated that you got 10 correct; however, you actually got 8 correct”); (3) after 3 consecutive sessions/days of high IA (+/- 1 discrepancy between actual correct and self-assessed), training then progresses to presentation of stimuli without trial-by-trial feedback wherein more global estimates are

trained; (4) In the final stage, response options are expanded to include a level of certainty rating, and these responses are connected to scoring to incentivize choice for high- and low-confident responses across levels of difficulty. Feedback is provided in the form of discrepancy and its direction (i.e., “*you guessed a number correct that was 3 words higher than what you actually got correct*”) which is translated to a score that is displayed in a “leaderboard” displaying progress during training. At the end of each session, questions ask what strategies the participant used to estimate their performance and what strategies could improve their score, with responses collaboratively developed with the Coach during coaching.

To deliver iTEST, we will use the NeuroUX platform, <https://www.getneuroux.com/>, a HIPAA compliant platform, for administration of iTEST. Information Technology infrastructure will securely collect the data gathered by smartphones and will store the information via transfer to an encrypted Amazon Web Service (AWS) server. AWS offers a simple and intuitive web-based user interface from user to server. It is an easy-to-use cloud computing platform that allows various storage services for backup, archiving, and disaster recovery use cases. AWS enables robust safeguards to help protect the privacy of the data with highly secure AWS Data centers. Specifically within AWS, data will be stored in the Amazon S3 service and will be used for large-scale analytics. Amazon S3 provides scalable and durable object storage in the cloud. S3 is where the experimenters will be storing the user information (phone number, start and end time) along with the survey links. Once the data is generated, the data will be stored securely in this server, which will only be accessible by study staff. The transmitted program elements are encrypted and separated from any identifiable information. No information is stored locally on the smartphone device and cannot be accessed by anyone if the device will be lost or stolen. The developer wrote a whitepaper for Institutional Review Boards that gives an executive summary of Amazon Web Service’s security: <https://aws.amazon.com/whitepapers/>.

The research team will input the participant’s phone number and the time of delivery of messages using an onboarding platform from Twilio. The onboarding platform passes the phone number and the delivery time windows to Dynamo DB (HIPAA Compliant), which then passes the info to a message queuing service, Amazon SQS (HIPAA Compliant). The NeuroUX platform then passes the queued messages to a cloud communications platform, Twilio (HIPAA Compliant). The same message is then forwarded to the downstream providers and to the destination carrier for the last leg of message delivery. With the scheduling dashboard, messages will have the option to be sent to email and/or to text messages.

As the training program is not an application on a smartphone, rather a hyperlink sent through an encrypted link to the text messages application, the assessments and cognitive training qualifies as a non-significant risk under FDA regulations and is experimental/investigational. The training is exempt from

IDE regulations for the following reasons, following recent 2022 FDA Policy for Device Software Functions and Mobile Medical Applications:

- 1) The software is not intended as an implant, nor does it support or sustain human life.
- 2) The use of the software is not important in diagnosing, curing, mitigating, treating disease, or preventing the impairment of health.
- 3) The software does not cause significant harm to subjects – nor is it life threatening, cause permanent impairment of a body function, cause permanent damage to a body structure, nor could it necessitate

medical or surgical intervention to preclude permanent impairment of a body function or preclude permanent damage to body structure.

- 4). The participants will complete cognitive testing for the training and are not obligated to complete each survey session if they do not want to.
- 5). The training is not intended to be used for diagnostic purposes.
- 6). The training does not interact with any medical devices and does not impact the functionality or performance of traditional medical devices.
- 7). Furthermore, no blood draws or invasive collection methods will be used by the study owned smartphones or the participant's personal smartphones.
- 8) The subject does not need to go undergo any invasive procedures as part of the study.
- 9). The smartphone is used by the participant's fingers and will not enter the participant's body nor does it involve a break in skin, have contact with the mucous membrane or internal body cavity

Additional Screenshots of the software are attached to this protocol.

Transportation: For participants who are unable to meet in our research office space due to physical disability or financial reasons, we will use the UCSD Lyft Concierge service for transportation, provided that residence is within a 25-mile radius of UCSD. Participants will **NOT** be required to pay for the Lyft rides as the research study will cover the costs of these rides.

To use Lyft participants will be providing name, pick-up location, drop-off location, and phone number to the research staff, which will then be used by the Lyft driver. This information will only be given to the Lyft drivers after consent over the phone (during the phone screening procedures) and by providing written consent in the Informed Consent document. Participants phone number and the driver's phone number will be masked during the active ride through a third party system. Neither participant nor the driver will have access to each other's real phone numbers. Personal health information (PHI) will not be shared with Lyft.

If participants choose to their own mode of transportation, they are subject to any associated to charges or fees, however, they will not be required to pay for parking at our research office for the duration of the visit.

Compensation for assessments and screening:

Participants are paid up to \$220.00 for in-lab assessments. A total of \$20 is provided for completing the screening portion of Visit 1 and participants are compensated \$50 for completing the rest of that visit. For Visit 2, 3, and 4 participants are compensated \$50 for each.

We also have assessments delivered through the mobile device at Baseline (Visit 1) and each of the weeks that coincide with lab visits (i.e., weeks 9, 13, and 17).. Assessments will involve 6 days of completing brief mobile assessments that closely mirror the iTEST training, and participants will be paid 5 dollars for each of the 6 mobile assessments that they complete. The number of days completed is factored to the compensation and so participants can receive up to 30 dollars for completing all 6 assessments. Thus, over four assessment days, participants can be compensated up to 120 dollars (30 x 4 assessments).

Combining in-lab and mobile assessments, the maximum possible amount of compensation is \$340.

Notably, participants are not compensated for meeting with the coach or for completing the training exercises on the mobile device. If participants choose to stop attending meetings with the coach or completing the mobile exercises, they may continue to participate in other aspects of the study and continue to receive compensation as above.

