8 STUDY ASSESSMENTS AND PROCEDURES

8.1 EFFICACY ASSESSMENTS

Primary Targets: In addition to adherence, the primary Go/No Go targets of the R61 include both IA on trained (METER, VLMT) and untrained task (WCST). During each VLMT and Meter administration, participants are presented with 3 trials where lists of words or faces are presented. For the VLMT, immediately following each exposure to the list, participants were shown target and recognition foil words one-by-one and asked to indicate whether or not the word appeared on the list. For the METER task, participants are asked to guess the emotion in a picture of a human face from among anger, sadness, happiness, no emotion, or fear. After completion of the task, scoring includes the percentage of correct identifications of target words or faces per trial. In embedded validity tests, after each administration, participants self-reported if they were distracted or interrupted.

The reason that trained tasks are part of our Go/No Go criteria is because lack of improvement on trained tasks would call into question the ability of iTEST to modify IA, and would indicate need for program revisions. IA is calculated as the discrepancy (absolute) between each trial's correct performance from that estimated by the participant, which is nested within sessions and weeks. IA on the VLMT and METER tasks predict functional outcomes and is stable over time without training.

An additional Go/No Go component is transfer of training to an untrained task-based measure of IA, the Meta-Cognitive Wisconsin Card Sorting Test¹³. Wisconsin Card Sorting Task (WCST) (Heaton, Chelune, Talley, Kay & Curtiss, 1993). The WCST is a widely used measure of executive function that requires participants to match a presented card to one of four stimulus cards. There are several ways in which the card could be successfully sorted but participants are not informed of the criterion they should use to match the card. Instead, feedback is given after each sort (i.e. correct or incorrect), and participants must use this information to adjust their responses. After each sort, participants are asked to provide a judgement of correctness which are aggregated across sorts and used as the indicator of IA. IA on this task is also associated with functioning and improvement on this task would support that iTEST leads to

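### On the VLMT, answering yes to every word and reporting the list length gives a zero IA gap without introspection, and no validity rule or sensitivity analysis would reveal it

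*Combined protocol and SAP*

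**What the plan says.** **Task and endpoint.** In Section 8.1, VLMT participants are "shown target and recognition foil words one-by-one and asked to indicate whether or not the word appeared on the list". Performance is described only as follows: "scoring includes the percentage of correct identifications of target words or faces per trial". The endpoint rule in the same section is that "IA is calculated as the discrepancy (absolute) between each trial's correct performance from that estimated by the participant". Section 6.1.1 adds that the judgement asked for is the number of words or faces correct, with confidence.

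**Training (6.1.1).** Practice rounds are repeated for anyone who might "mistake performance vs. IA accuracy as the basis of scoring". Step 1 trains the participant to state how many stimuli were shown. Moving on to step 3 needs a gap of at most 1 in three consecutive sessions, and no minimum performance is set. Feedback is the size and direction of the gap, converted to a leaderboard score. In step 4, certainty ratings also enter the score. Each session ends by asking "what strategies the participant used to estimate their performance and what strategies could improve their score", and the answers are worked on with the coach. The paid mobile assessments at baseline and at the later visits are described as very similar to the training.

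**Checks and analysis.** Sections 2.2 and 8.1 describe one validity check, a self-report of distraction or interruption. No section gives a rule on false alarms, constant responding or minimum accuracy. Section 9.4.1 models IA as the slope of judgement on objective performance, not as the absolute gap.

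**Decision rule (Section 3).** A *go* needs at least 75% adherence, d above 0.50 on both trained tasks, and d above 0.50 on the WCST.

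**The concern.** The gap measures introspection only while the participant is trying to do the memory task. If the answers are fixed in advance, the number correct is known in advance too, and judging it needs no self-monitoring. The training favours a small gap, teaches the one number needed (list length) and sets no performance floor.

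The incentive starts after baseline, so any uptake would push the pre-post change one way, towards success. There is no comparator arm to expose it. Adherence counts completed sessions, so these sessions would also count as adherent. At stake is what a VLMT result above 0.5 can be claimed to show, and whether the VLMT appears to reach its threshold at an earlier week.

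**Working it through.** The plan states no figure on this point, so there is nothing to reproduce. The check applies the plan's scoring rule directly.

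**1. The gap on the VLMT (8.1 definition).** Let L be the number of listed words and F the number of foils. Neither is given, so L = 4 to 20 and F = 0.5L to 2L were assumed, with each listed word tested once. The participant answers *yes* throughout and reports L. Hits = L and correct rejections = 0.
- If only targets count: actual correct = L, gap = |L − L| = 0.
- If all items count: actual correct = L + 0 = L, gap = 0.

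For example, with L = 12 and F = 12 there are 12 hits, 0 correct rejections and 12 reported, so the gap is 0. The hit rate is 12/12 = 1 and the false-alarm rate is 12/12 = 1, so there is no discrimination. The zero holds for every L and F tried.

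It does depend on all listed words being tested, which 8.1 suggests but does not state. If only 75% of 12 words were tested, the gap would be 12 − 9 = 3; at 50% it would be 12 − 6 = 6. Under target-only scoring, answering *no* throughout and reporting 0 gives a zero gap without that assumption.

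**2. The slope (9.4.1).** The result depends on a metric that the plan does not fix.
- Counts: judgement = L and performance = L, and 6.1.1 says the number of stimuli varies. Slope = cov(L, L)/var(L) = 1, which reads as perfect tracking.
- Percentages: performance is 100% on every trial (targets only) or L/(L + F), which is 50% if F = L. After centring on the week's mean the variance is 0, so that person-week's slope is 0/0 and cannot be estimated.

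**3. METER.** Choose one emotion of the five throughout and report L/5 rounded, assuming equally likely emotions. By simulation the mean gap is 0.72, 1.09 and 1.38 faces for L = 6, 12 and 18. For scale, an honest respondent with assumed 80% accuracy and an assumed estimation error of SD 2 has mean gaps of 1.16, 1.38 and 1.49. The exact zero does not carry over, and any METER gain would be partial.

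**4. Size on the gap measure.** Suppose a share f of participants move to a zero gap and the rest do not change. Let m be the mean baseline gap and CV = SD/m across persons. Section 9.1 divides by the baseline SD, so d = f·m/SD = f/CV.

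| Assumed CV | d at f = 10% | f giving d = 0.5 (0.5 × CV) |
|---|---|---|
| 0.4 | 0.10/0.4 = 0.25 | 20% (12 of 60) |
| 0.5 | 0.10/0.5 = 0.20 | 25% (15 of 60) |
| 0.6 | 0.10/0.6 = 0.17 | 30% (18 of 60) |
| 0.8 | 0.10/0.8 = 0.13 | 40% (24 of 60) |

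If the remaining participants have a real effect d₀, the observed d is (1 − f)·d₀ + f/CV. With f = 10% and d₀ = 0.3, this is 0.27 + 0.25 = 0.52 at CV 0.4, but 0.27 + 0.125 = 0.40 at CV 0.8. Both f and CV are assumptions; the documents give neither.

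**The case against.** The strongest reply is that nothing in the documents shows anyone would respond this way. Training is unpaid, and the mobile assessments are paid for completion, not score. Strategy answers are developed with a supervised coach who reviews IA scores, and sessions are rated against an 80% fidelity threshold. This stands as far as frequency goes. It is not a screen, however: fidelity ratings assess the coach, and 6.1.1 schedules an introductory session and five weekly ones within a 16-week intervention.

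A second reply is that objective performance already enters the 9.4.1 model. That is correct, and it would be wrong to say that accuracy is ignored. But as a predictor it does not identify these blocks: on counts they look like perfect tracking.

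Stronger readings that a reader might infer are not supported:
- *Training scores only the gap.* Step 1 scores the number of stimuli and step 4 brings in certainty ratings, so even the training score need not be perfect.
- *The behaviour always scores as perfect IA.* This is true of the gap, and of a slope on counts with varying list length, but not of a slope on percentages.
- *It could deliver a go.* METER is at most partly affected, and the WCST and adherence criteria must also be met.
- *Flagged blocks should be removed from the primary estimate.* Excluding data on post-baseline behaviour fits poorly with the intention-to-treat statement in 9.3. A rule for identical responses would also be evaded by a single different answer.

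**Conclusion.** The point holds in limited form. By the plan's own absolute-gap definition, a fixed response style gives the best possible VLMT score with no introspection, and no planned check would show it. The result is exact if every listed word is tested once. The consequence for the 9.4.1 slope depends on whether performance is analysed as counts or percentages.

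The bias would favour success on one of the two tasks in the second criterion, and on the VLMT part of the duration reading in 9.4.3. Its size is unknown. Reaching d = 0.5 from this source alone would take 20% to 40% of participants over the CV range shown; a smaller uptake matters mainly when the real effect is already near the threshold. This is a gap in what the VLMT result can demonstrate, not evidence that the trial will mislead.

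**What to change.** Add to 8.1 and 9.4.1:
- At baseline and at each assessment, report the VLMT hit rate and false-alarm rate, and METER accuracy, beside d.
- Report the share of VLMT and METER blocks in which every item received the same response.
- Prespecify a sensitivity estimate of d that excludes those blocks at every assessment, including baseline.
- Keep the all-blocks intention-to-treat estimate as primary. State that a VLMT d above 0.5 will not be attributed to improved IA if it falls below 0.5 without those blocks.
- State whether performance enters the 9.4.1 model as a count or a percentage, and whether every listed word is tested.

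The cost is a little extra analysis and text, with no added participant burden. Some genuine low-effort blocks will be dropped from the sensitivity estimate. Near-constant responding will escape the block rule, which is why the hit, false-alarm and accuracy figures are needed as well. All of this depends on the platform keeping item-level responses. The documents imply this through trial-by-trial feedback but do not state it, so it should be confirmed with the vendor.
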